5.5.3 Laboratory Data

Routine clinical laboratory findings will be summarized using descriptive statistics for each treatment group. Changes from baseline to each visit will be determined for quantitative variables.

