# 7.3 Withdrawal, Removal, and Replacement of Participants

A participant may voluntarily withdraw or be withdrawn from the study at any time for reasons including, but not limited to, the following:

- Progression of disease: Either unequivocal symptomatic progression necessitating a change in therapy in the opinion of the treating physician or radiologic progression as defined by cross-sectional imaging utilizing RECIST 1.1 criteria.
- Treatment Cessation: Discontinuation criteria apply for all drug-related AEs attributed to nivolumab, ipilimumab or both. Treatment with all study drugs should be permanently discontinued for the following:
  - Any Grade 2 drug related uveitis or eye pain or blurred vision that does not respond to topical therapy and does not improve to Grade 1 severity within the re-treatment period OR requires systemic treatment
  - o Any Grade 3 non-skin, drug-related AE, with the following exceptions:
    - Grade 3 diarrhea lasting <7 days
    - Grade 3 drug-related laboratory abnormalities do not require treatment discontinuation except
      - ➤ Grade 3 drug-related thrombocytopenia >7 days or associated with bleeding requires discontinuation
      - Any drug-related liver function test abnormality that meets the following criteria requires discontinuation:
        - AST or ALT >8 x upper limit of normal (ULN)
        - Total Bilirubin >5x ULN
        - Concurrent AST or ALT and total bilirubin >2x ULN
  - Any Grade 4 drug-related AE or laboratory abnormality, except for the following events which do not require discontinuation.

- Grade 4 amylase or lipase abnormalities that are not associated with symptoms or clinical manifestations of pancreatitis.
- Isolated Grade 4 electrolyte imbalances/abnormalities that are not associated with clinical sequelae and are corrected with supplementation/appropriate management within 72 hours of their onset
- Any dosing interruption lasting >6 weeks with the following exceptions:
  - Dosing interruptions to allow for prolonged steroid tapers to manage drugrelated AEs are allowed.
  - Dosing interruptions >6 weeks that occur for non-drug related may be allowed if approved by the primary Investigator
- Any AE, laboratory abnormality or intercurrent illness which, in the judgment of the Investigator, presents a substantial clinical risk to the participant with continued drug dosing.
- Withdrawal of consent: Participant may withdraw consent at any time.
- Death

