#### 8.2 Toxicities / Side Effects

## 8.2.1 Ipilimumab

Likely Side Effects: Diarrhea, inflammation of the colon (colitis), increase in liver enzymes, fatigue, skin itchiness, skin rash, nausea, abdominal pain, decreased appetite, fever, vomiting, headache, constipation, adrenal gland abnormalities, and thyroid gland abnormalities.

Less Likely Side Effects: Chills, weakness, muscle pain, and redness of skin.

Rare Side Effects: Decrease or total loss of hormones of pituitary gland, allergic reactions, inflammation of the liver, inflammation of the pituitary gland, decreased red blood cells, loss of color (pigment) from areas of skin, decreased or blurry vision, or inflammation of the eye, numbness or tingling in your fingers or toes, inflammation or loss of the lining of the brain or spinal cord, inflammation of the kidneys, and joint pain.

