<sup>gTSH will be checked at every visit and will reflex to check free T4 if abnormal.

<sup>hPer standard of care to provide data for RECIST measurements as appropriate for each participant per the investigator physician. CT scans will be performed at baseline (-7 days), Week 12, Week 18, and every 12 weeks (±7 days) thereafter until progression of disease, death, or end of study for up to 2 years. A CT scan of the chest, abdomen and pelvis or an MRI of the abdomen and pelvis plus a non-contrast CT of the chest are acceptable.

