## 11.1.2 Serious Adverse Events

An AE is considered serious if it results in any of the following outcomes:

- Death
- A life-threatening AE
- An AE that results in hospital admission or prolongation of existing hospitalization

- A persistent or significant incapacity or substantial disruption of the ability to conduct normal life functions
- A congenital anomaly/birth defect
- Important Medical Events that may not result in death, be life threatening, or require hospitalization may be considered serious when, based upon medical judgment, they may jeopardize the participant or subject and may require medical or surgical intervention to prevent one of the outcomes listed in this definition
- Potential drug induced liver injury (DILI) is also considered an important medical event. DILI is defined as the following:
  - o ALT or AST elevation >3x ULN AND
  - Total bilirubin >2x ULN, without elevated serum alkaline phosphatase AND
  - No other immediately apparent possible causes of AST/ALT elevation and hyperbilirubinemia, including, but not limited to, viral hepatitis, pre-existing chronic or acute liver disease, or the administration of other drug(s) known to be hepatotoxic.

Suspected transmission of an infectious agent (e.g., pathogenic or nonpathogenic) via study drug is an SAE.

Although pregnancy, overdose, and cancer are not always serious by regulatory definition, these events must be handled as SAEs.

Note: Hospital admission for elective pre-planned surgeries is not considered an SAE.

Disease Progression is considered a non-reportable event.

SAE reporting is required as soon as the participant signs consent and is registered. SAE reporting is required for 100-days after the participant's last investigational treatment or intervention. Any events that occur after the 100-day period and that are at least possibly related to protocol treatment must be reported.

inVentiv Health Clinical will manage SAEs using ARGUS, and all sites will send reports to inVentiv's safety team via email. Sites will not upload any reports directly into ARGUS.

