5 STATISTICAL METHODS

Summary statistics will be presented by treatment arm. For continuous variables, data will be summarized with the number of participants (N), mean, standard deviation, median, minimum, and maximum. For categorical variables, data will be tabulated with the number and proportion of participants for each category.

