5.5 Safety Analysis

Safety will be assessed through the summary of adverse events (AEs), serious adverse events (SAEs), laboratory test results (hematology and serum chemistry), vital signs, and physical examinations. Safety summaries will include endpoints as described in Section 3.3.2. This may include data collected at unscheduled visits, early termination visits, or follow-up visits.

Safety outcomes will be summarized based on the safety-evaluable population (see Section 5.1.2). Safety summaries will be presented by treatment arm.

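### The by-visit laboratory summaries in SAP 5.5.3 cannot give a per-arm count of participants reaching a CTCAE grade or a protocol hepatic threshold, and SAP 5.5 does not say whether TSH and free T4 are covered

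*SAP*

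**What the plan says.** SAP 5.5.3 has two sentences: "Routine clinical laboratory findings will be summarized using descriptive statistics for each treatment group", and "Changes from baseline to each visit will be determined for quantitative variables". The general rule in SAP section 5 fixes what descriptive means: "For continuous variables, data will be summarized with the number of participants (N), mean, standard deviation, median, minimum, and maximum". SAP 3.3.2 defines the laboratory part of the safety endpoint as change from baseline. No table of grades, shifts, worst post-baseline values, ULN multiples or threshold counts is planned.

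SAP 5.5 describes the laboratory data as "laboratory test results (hematology and serum chemistry", and says that unscheduled, early termination and follow-up data may be included, without requiring it.

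The protocol judges hepatic safety by grade and by ULN multiple:
- Section 7.3 lists "AST or ALT >8 x upper limit of normal (ULN"), total bilirubin above 5x ULN, and a concurrent AST or ALT and bilirubin criterion at 2x ULN.
- Section 11.1.2 states that "Potential drug induced liver injury (DILI) is also considered an important medical event", and defines it by AST or ALT above 3x ULN with bilirubin above 2x ULN plus further conditions.
- Section 8.4.2 makes the hepatic dose-delay grade depend on whether the baseline value was normal or Grade 1.

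Protocol 8.2 lists raised liver enzymes as likely with both regimens. For ipilimumab the likely effects include "adrenal gland abnormalities, and thyroid gland abnormalities"; thyroid inflammation is listed as less likely with the combination. Table 3 gives thyroid testing its own row, with the footnote "TSH will be checked at every visit and will reflex to check free T4 if abnormal".

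**The concern.** The protocol's laboratory safety questions concern participants: did this person cross a limit, did two analytes rise together, how far did the grade move from baseline? The planned laboratory tables describe visits, one analyte at a time. A set of by-visit statistics does not determine the number of distinct participants who crossed a limit at any time.

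This matters because the study's stated purpose (SAP 3.4) is to give preliminary estimates, including of adverse events, with about 12 participants per arm. A per-arm n/N for hepatic and thyroid abnormalities is a natural output of such a study. Under the plan, that number would come only from what investigators chose to report as adverse events. For thyroid function, collected at every visit, the SAP does not say whether the laboratory values are summarised.

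**Working it through.** **Reproducing the plan's figures.** The nearest stated figures are the exact intervals in SAP Table 1. The two-sided 95% Clopper-Pearson limits for x of n = 12 are the 0.025 quantile of Beta(x, n − x + 1) and the 0.975 quantile of Beta(x + 1, n − x). All six rows match to one decimal, including 1/12 (0.2% to 38.5%) and 3/12 (5.5% to 57.2%). For 0/12, which is not in Table 1, the upper limit is 1 − 0.025^(1/12) = 26.5%.

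**Illustration 1: counting participants.** Assumed values, not document figures: 12 participants, all with baseline ALT 0.6x ULN and unchanged except where stated. At each of three visits exactly one participant is at 8.5x ULN. For each visit:
- Mean change = (8.5 − 0.6)/12 = 7.9/12 = 0.66x ULN; mean value = 0.6 + 0.66 = 1.26x ULN.
- SD of change = 7.9/√12 = 2.28x ULN; this form holds for one non-zero value among 12.
- Median change = 0.
- Minimum change = 0; maximum change = +7.9x ULN; maximum value = 8.5x ULN.

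The maximum reveals the event. But these nine rows (three visits, three events in total) are the same in two different cases:

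| Case | Participants above 8x ULN | Exact 95% CI |
|---|---|---|
| One participant, high at all three visits | 1/12 (8.3%) | 0.2% to 38.5% |
| Three participants, one at each visit | 3/12 (25.0%) | 5.5% to 57.2% |

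**Illustration 2: pairing analytes.** Suppose one visit shows a maximum ALT above 3x ULN and a maximum bilirubin above 2x ULN. If both belong to one person, the AST/ALT and bilirubin parts of the 11.1.2 definition are met in 1/12. If they belong to two people, they are met in 0/12 (0% to 26.5%). Separate tables for each analyte are identical either way. The same holds for the concurrent criterion in 7.3.

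**Illustration 3: TSH.** Baseline 2 mU/L in all 12; one rises to 6 and two fall to 0.05. Mean change = (4 − 1.95 − 1.95)/12 = 0.1/12 = 0.01; median 0; minimum −1.95; maximum +4. The extremes show movement in both directions. Neither the mean nor the extremes show that 3/12 moved out of range (assuming the local range excludes 6 and 0.05).

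**How often there would be something to count.** The chance of at least one affected participant in an arm of 12 is 1 − (1 − p)^12. For assumed true rates of 5%, 10% and 20% this is 46%, 72% and 93%.

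**Units.** SAP 5.5.3 does not say whether values are scaled to ULN. Eligibility uses each institution's own ULN, and the trial has several sites, so a maximum reported in raw units would not convert to the multiples in 7.3 and 11.1.2.

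**The case against.** The strongest case on the other side is that these harms are already analysed elsewhere. Protocol 11.1.1 allows an abnormal laboratory finding to be an adverse event. SAP 5.5.2 tabulates treatment-emergent events by arm, by worst grade, by relatedness, by seriousness and by discontinuation of treatment. Potential drug-induced liver injury falls under the serious event definition, and a drug-related AST or ALT above 8x ULN requires discontinuation under 7.3. If the three events in the first illustration were drug-related, occurred during dosing and were reported, the discontinuation table should show 3/12. Protocol 8.4.2 also has investigators review laboratory values before each dose. This stands as an answer to any claim that the harms go unanalysed.

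It does not supply an objective count. That route depends on each investigator reporting a value as an event. Section 7.3 does not require discontinuation for most Grade 3 laboratory abnormalities, so that table is not a reliable substitute. The SAP explicitly relies on adverse events for physical examinations (5.5.5) but keeps laboratory results as an analysis of their own.

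A reader might infer several stronger points that the documents do not support:
- **That only changes are summarised.** SAP 5.5.3 also summarises the values themselves.
- **That harms are averaged away.** Minimum and maximum are planned, so an extreme value included in the table remains visible.
- **That thyroid tests are excluded.** The wording of 5.5.3 is broad enough to include TSH, protocol 9.2.2 lists TSH and free T4 beside the blood count and metabolic panel, and protocol section 12 says all data will be listed. The gap is one of naming.
- **That participants who stop for toxicity disappear.** Table 3 schedules laboratory tests at Follow-up Visits 1 and 2 and at early termination.
- **That abnormal baselines dominate the mean changes.** Inclusion criterion 9f permits raised AST/ALT with liver metastases, but nothing here shows that effect; the illustration uses one common baseline.

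**Conclusion.** The point holds as a gap in what the laboratory tables can answer, and closing it is a cheap improvement. The plan's by-visit statistics detect that an extreme value occurred; they do not give the number of participants per arm who reached a grade or a protocol hepatic threshold, nor whether AST/ALT and bilirubin rose in the same participant. In the illustration, identical tables are compatible with 1/12 and 3/12. Inclusion of unscheduled values is optional, so a peak seen only at such a visit may or may not appear. Coverage of TSH and free T4 is unstated.

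The size is modest: this is a descriptive safety analysis of 24 participants, and neither the sample size nor the efficacy analysis is affected. The conclusion assumes that AST, ALT and bilirubin belong to the chemistry panel, whose contents the documents do not list. The ALT and TSH values are assumed for illustration.

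**What to change.** Before database lock, since SAP section 2 allows no changes at or after it, keep the by-visit change-from-baseline summary, which is the endpoint in SAP 3.3.2. Add to SAP 5.5.3, by arm:

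1. A shift table from baseline to worst post-baseline CTCAE v4.0 grade for each gradable analyte, through last dose plus 100 days, using all scheduled and unscheduled values.
2. n/N meeting each existing protocol hepatic threshold, scaled to the local ULN: AST/ALT above 3x and above 8x; total bilirubin above 2x and above 5x; the 7.3 concurrent AST/ALT and bilirubin criterion at 2x; and the 11.1.2 laboratory combination. Combinations should be paired within participant.
3. n/N newly below or above the local normal range for TSH and for free T4, with both tests named in SAP 5.5. A note should say that after screening free T4 is measured only as a reflex to an abnormal TSH, so its denominator is a selected group.

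The cost is SAP wording and two or three extra tables. Local reference ranges and unscheduled laboratory values must be in the database, which the documents do not confirm. No new tests are needed, and no clinical threshold or management rule changes.

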5.5.4 Vital Signs

Vital signs at each visit and change from baseline to each post-baseline visit will be summarized using descriptive statistics for each treatment arm.

5.5.5 Physical Examinations

Physical examination data will not be summarized because any significant findings should be captured and summarized as adverse events.

5.6 Missing Data

5.6.1 Missing and Partial Missing Adverse Event Dates

Partially missing data of AE onset date may be imputed in order to avoid eliminating information from summary tables of TEAEs. If the day of an AE onset date is missing but both the month and year are available, the AE will be flagged as treatment-emergent if the date is conservatively estimated to be within 100 days after the last dose of study drug administration. Any AE deemed related to study drug will also be considered a TEAE regardless of elapsed time since last study drug administration. There will be no attempt to impute missing or partially missing dates for the listing of AEs.

5.6.2 Partial Missing Death Dates

For death dates, the following conventions will be used for imputing partial dates:

- If only the day of the month is missing, the 1st of the month will be used to replace the missing day. The imputed date will be compared to the last known date alive plus 1 day, and the maximum will be considered as the death date.
- If the month or the year is missing, the death date will be imputed as the last known date alive plus 1 day.
- If the date is completely missing but the reason for death is present, the death date will be imputed as the last known date alive plus 1 day.

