**Table 3: Schedule of Assessments** 

	Baseline/ Screening a	Cycle 1 b	Cycle 2	Cycle 3	Cycle 4	Follow-up Visit 1 and 2 d	Additional Follow-up Visits e	Early Termination Visit f
Obtain Informed Consent	X							
Participant History	X							
Inclusion/Exclusion criteria	X							
Biopsy of Target Lesion c	X	X						
Prior/concomitant medications	Collected from Screening to Follow-up							
Physical Examination	X	X	X	X	X	X		X
Performance status	X	X	X	X	X	X		X
Height/Weight	X	X	X	X	X	X		X
Vital Signs	X	X	X	X	X	X		X
Complete Blood Count	X	X	X	X	X	X		X
Complete Metabolic Panel, LDH	X	X	X	X	X	X		X
Thyroid function testing g	X	X	X	X	X	X		X
Pregnancy test (serum)	X	X	X	X	X	X		X
HCV, HBV, HIV Testing	X							
CT scan h	X				X	X		X
MRI Brain	X							
ECG	X							
Adverse Events	Collected from consent to 100 days after drug discontinuation							
Drug Administration		X	X	X	X			
Research blood (~40mL)	X	X	X	X	X	X		X

PD-L1 expression on banked tumor specimen if available	X					
Survival Data				X	X	X

<sup>aScreening assessments are recommended to be performed within 28 days prior to treatment unless otherwise specified above

<sup>bEach cycle=21 days±4 days

<sup>cBiopsy at baseline for all participants within 14 days of Cycle 1, Day 1. On-treatment biopsy must be performed within 14 days±5 days of first dose of study drug.

<sup>dFollow up period begins when the last dose of study therapy is administered. Follow-up visit 1=21 days from last dose  $\pm$  7 days. Follow-up visit 2=42 days from last dose  $\pm$  7 days. If the participant completed follow-up visit 1 and follow-up visit 2 and *has* progressed, the participant is not required to have scans every 12 weeks. Survival could be assessed via calls every 3 months ( $\pm$ 7 days). If a participant is off treatment and *has not* progressed, they would continue to visit the site and have scans every 12 weeks.

 $^{\rm e}$ Additional follow-up visits will be scheduled every 3 months  $\pm 7$  days. For participants who end treatment for toxicity, scans should continue every 12 weeks until progression of disease. After progression of disease, survival calls will occur every 3 months ( $\pm 7$  days).

<sup>fFor participants who terminate the study early, follow-up will begin 21 days from the last dose (follow-up visit 1).

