5.4.2 Secondary Efficacy Endpoints

Disease Control Rate

DCR is defined as the proportion of participants who achieve SD, PR, or CR as measured by RECIST v1.1. That is, DCR is the number of participants whose BOR is SD, PR, or CR divided by the total number of participants in the population of interest. For SD, measurements must have met the SD criteria per RECIST v1.1 at least once after study entry, with disease assessment occurring at least 8 weeks after first study drug treatment.

DCR will be assessed at Week 12 (+7 days) and Week 18 (+7 days). DCR will be estimated within each treatment arm and 95% confidence intervals (CIs) will be estimated using the Clopper-Pearson method.

This study is not powered for statistical comparisons between arms. To aid in interpretation, each arm will be indirectly compared to the historical ipilimumab DCR of 28.5% (Hodi et al. 2010).

Time to Treatment Failure

TTF is defined as the time from first study drug treatment until the participant is started on another line of systemic therapy or participant death, whichever occurs first. Participants who are alive and do not start another therapy will be censored at the date of last follow-up. Time to event distributions will be estimated using Kaplan-Meier techniques.

Overall Survival

OS is defined as the time from first study drug treatment until death from any cause. Participants without documentation of death will be censored on the date of last contact. Time to event distributions will be estimated using Kaplan-Meier techniques.

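### SAP 5.6.2 ignores a recorded year of death when the month is missing, so the imputed date can fall in an earlier year than the record allows

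*SAP*

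**What the plan says.** SAP 5.6.2 gives three rules for incomplete death dates.

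- **Only the day is missing.** The 1st of the recorded month is inserted, and then: "The imputed date will be compared to the last known date alive plus 1 day, and the maximum will be considered as the death date".
- **Month or year is missing.** "If the month or the year is missing, the death date will be imputed as the last known date alive plus 1 day". There is no comparison with any part of the date that is known.
- **Date completely missing.** The same date, last known date alive + 1 day, is used, but with a condition: "If the date is completely missing but the reason for death is present".

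SAP 5.4.2 sets the endpoints that use these dates. For OS, "OS is defined as the time from first study drug treatment until death from any cause", and "Participants without documentation of death will be censored on the date of last contact". TTF runs "until the participant is started on another line of systemic therapy or participant death, whichever occurs first". Both are summarised by Kaplan-Meier methods.

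SAP 5.6.3 has separate rules for treatment failure dates. A failure date that lacks day and month, or is wholly absent, is treated as missing. A failure date lacking only the day is compared with the death date only if that death date is complete. Neither section says which one governs when the failure is the death itself.

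On data collection, Protocol Table 3 (footnote d) says of participants who have progressed: "Survival could be assessed via calls every 3 months", with a 7-day window either side. Protocol 11.1.5 puts every death on a Death eCRF page.

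**The concern.** The first rule never contradicts the form, because it treats the recorded month as a lower bound. The second rule drops that bound. If a relative reports on a survival call that the participant died in a given year but cannot give the month, the year is real information, and the imputed date can fall before that year began.

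The third rule raises a drafting question. Cause of death is irrelevant to an all-cause endpoint, so it is unclear why a recorded reason should decide whether a date is imputed.

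Death is the OS event and one of the two TTF events. Follow-up by telephone after progression is a setting in which incomplete dates can plausibly arise. SAP 5.4.4 plans no sensitivity analyses, and SAP section 2 allows no change at or after database lock, so the rule should be right beforehand.

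**Working it through.** The plan states no figure that depends on this rule, so there is nothing to reproduce. The check applies the rules literally and compares them with the first rule's own logic extended to a known year.

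**Inputs.** The rules of SAP 5.6.2; contact every 3 months ± 7 days (Protocol Table 3); 12 participants per arm (SAP section 3). The calendar dates below are hypothetical.

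**Formulas.** A = last known date alive; Y = recorded year of death, month missing.

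- SAP rule: A + 1 day.
- Year-aware rule: the later of 1 January of Y and A + 1 day.
- Shift = year-aware date minus SAP date. It is above zero exactly when A + 1 day falls before 1 January of Y, that is, when A is in an earlier year and is not 31 December of the year just before Y.

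**Worked dates, death recorded as 2019**

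| Last known alive | SAP date | Year-aware date | Shift |
|---|---|---|---|
| 1 Oct 2018 | 2 Oct 2018 | 1 Jan 2019 | 91 days |
| 15 Nov 2018 | 16 Nov 2018 | 1 Jan 2019 | 46 days |
| 31 Dec 2018 | 1 Jan 2019 | 1 Jan 2019 | 0 |
| 20 Jan 2019 | 21 Jan 2019 | 21 Jan 2019 | 0 |

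The shift is never negative, so the error can only shorten survival. For contrast, if only the day were missing and the form said January 2019, the first rule would give 1 January 2019 for the 15 November case. Knowing less about the date moves it outside the recorded year.

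**Upper bound when contact is kept.** Three months is about 91 days. With 7 days' slack at each end, two contacts are at most about 91 + 14 = 105 days apart. Death in Y is learned no later than the next contact, so A is at most 105 days before 1 January of Y, and the shift is at most 105 − 1 = 104 days, about 3.5 months. A longer shift needs missed contacts.

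**How often, given a death with year known and month missing.** Assume the day of death is uniform over the year and the time since last contact is uniform from 0 to L days. Then

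- share with a wrong year = (L − 1)² / (2 × 365 × L);
- mean shift among those = (L − 1) / 3.

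| L (days) | Share in wrong year | Mean shift |
|---|---|---|
| 91 | 90² / (730 × 91) = 12% | 90/3 = 30 days |
| 105 | 104² / (730 × 105) = 14% | 104/3 = 35 days |
| 183 | 182² / (730 × 183) = 25% | 182/3 = 61 days |
| 365 | 364² / (730 × 365) = 50% | 364/3 = 121 days |

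The documents do not say how many deaths will lack a month. If it were 0 to 2 per arm (an assumption), 91-day contact would give 0 to 2 × 0.12 = 0.24 wrong-year deaths per arm.

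**Second and third rules side by side.** A completely missing date also has its month missing.

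- If the second rule covers it, the third rule gives the same date and its condition on a reason has no effect.
- If the third rule alone covers it, a documented death with neither date nor reason has no imputation rule. It cannot be censored under SAP 5.4.2 either, since censoring is for participants without documentation of death.

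**The case against.** The best defence is that last known date alive + 1 day is a deliberately conservative convention. That does not rescue the second rule. The year-aware date is already the earliest date the record permits, so going earlier adds a contradiction and no further caution.

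The defence is stronger on size, and most of it stands. The error needs a missing month, a known year, and a last known alive date in an earlier year; otherwise the two rules agree. In the 15 November example the correctable error is 46 days, because the year-aware rule also chooses the earliest permitted date. A misdated death moves a Kaplan-Meier step sideways and does not add or remove one. OS and TTF are descriptive here, with no hypothesis test, and the primary response endpoint and the sample size are untouched.

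A reader might infer from the third rule that deaths without a recorded reason are lost from the analysis. With 6 deaths among 12, excluding one would move 2-year survival from 50.0% to 1 − 5/11 = 54.5%, and censoring one at last contact would give between 54.5% and 7/12 = 58.3%. The documents do not support that reading. SAP 5.6.2 does not say that a date is imputed only if a reason is present, the second rule can be read to cover the case, and SAP 5.4.2 censors only those without documentation of death.

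Nor do the documents say that undated deaths are dropped from TTF. The rule in 5.6.3 that treats a date as missing could be applied to a failure by death, but the SAP leaves open whether it is.

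**Conclusion.** The second rule of SAP 5.6.2 is wrong as written in one identifiable case: year of death known, month missing, last known alive in an earlier calendar year other than on 31 December. There it gives a date that contradicts the record and is inconsistent with the rule above it, shortening OS, and TTF where death is the failure event. The shift is at most about 104 days if 3-monthly contact is kept, and longer only if contacts are missed. The 12% share and 30-day mean shift rest on the uniform assumptions above; the number of deaths exposed to the rule is unknown.

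The condition in the third rule is an ambiguity to remove, not a stated loss of events. The relation between 5.6.2 and 5.6.3 for failure by death is unspecified and needs one sentence. Severity is minor.

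**What to change.** In SAP 5.6.2, replace the second and third bullets with:

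*If the month is missing and the year is known, use the later of 1 January of the recorded year and last known date alive + 1 day. If the year is missing or the date is completely missing, use last known date alive + 1 day, whether or not a reason for death is recorded.*

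In SAP 5.6.3, add:

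*When the treatment failure event is death, the death date from 5.6.2 is used. The rule that treats a date as missing applies only to start dates of subsequent therapy.*

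The cost is a few SAP sentences and a small change to the derivation code, made before database lock. No new data are needed.
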